*** Other Levels Of Review ***

7. Other Levels Of Review

1. University Radiation Safety

Protocols that involve non-standard of care radioactive materials (which includes the terms "radioisotopes", "radionuclides", "radiopharmaceuticals", and "nuclear medicine studies", e.g., "PET", "MUGA", "Zevalin", and/or specific radionuclides such as "F-18", "Tc-99m", "Th-201", "I-131", "Ra-223", "Y-90", etc.) will receive review by the Radiation Safety Officer (RSO) and/or Radiation Safety Committee (RSC). For information on how to submit for radiation safety review, see RSC instructions or contact the Radiation Safety Officer at [name].

Not Applicable

Yes, study involves radioactive materials (per instructions, submit to RSC before IRB)

Protocol Title: Evaluation of Hysterotomy Site after Open Fetal Surgery

2. Institutional Biosafety

Experiments involving the deliberate transfer of Recombinant or Synthetic Nucleic Acid Molecules (e.g., Gene Transfer), or DNA or RNA derived from Recombinant or Synthetic Nucleic Acid Molecules, or Microorganisms containing Recombinant or Synthetic Nucleic Acid Molecules and/or infectious agents (including select agents and toxins as defined by CDC and/or Animal and Plant Health Inspection Service (APHIS)) into one or more human research participants must be reviewed by the SLU Biological Safety Officer. Most of these protocols also require review and approval by the SLU Institutional Biosafety Committee (IBC). Please contact the SLU Biological Safety Officer at [name] for more information.

Not Applicable
Yes, study requires Institutional Biosafety review

3. Pharmacy, Therapeutics, Nutrition, and Transfusion (PTNT) Committee

Saint Louis University Hospital requires that all research involving the administration of medications within the hospital (including outpatient areas such as the Emergency Department, Outpatient Center, Saint Louis University Hospital-South Campus, etc.) be reviewed and approved by the Pharmacy, Therapeutics, Nutrition, and Transfusion (PTNT) Committee and that study drugs are received, stored, prepared, and dispensed by the Hospital's Department of Pharmacy Services. Please contact the Investigational Drug Services Clinical Pharmacist at [name] or [contact] for more information.

Not Applicable
Yes, study requires PTNT review

4. Saint Louis University Hospital

All research involving Saint Louis University Hospital, including inpatient or outpatient services and medical record access, requires approval from the Saint Louis University Hospital Research Review Committee prior to study initiation. This effort is coordinated through the Clinical Trials Office via eRS. This process is designed to facilitate compliance with state and federal regulations as they pertain to research in hospitals and clinical research billing. Documents should be submitted as soon as possible, or at the latest, concurrently with IRB submission. Please contact the Research Compliance Office at [name] or [contact] or the SLU Clinical Trials Office at [name] or [contact] for more information.

Not Applicable
Yes, study requires Saint Louis University Hospital review

5. SSMSL

All research involving SSMSL locations (including Cardinal Glennon), including inpatient or outpatient services and medical record access, requires approval from the SSM STL or SSM Cardinal Glennon Research Business Review (RBR) prior to study initiation. This process is designed to facilitate

Protocol Title: Evaluation of Hysterotomy Site after Open Fetal Surgery

compliance with state and federal regulations as they pertain to research in hospitals and clinical research billing. While researchers can begin to complete the SSM RBR form at any time, the form should not be submitted until the IRB and the CTO have approved the study. Please contact the SSMSL Office at [name] or [contact] for more information.

Not Applicable
 Yes, study requires RBR review

6. Does this project require registration on ClinicalTrials.gov, and/or is this project subject to the NIH GCP Training Requirement? (Select "Yes" if either apply)

Registration may be required if any of the following apply: 1) The project meets the FDAAA definition of an "[Applicable Clinical Trial](https://prisinfo.clinicaltrials.gov/ACT_Checklist.pdf)", which requires registration on ClinicalTrials.gov.; 2) As of January 1, 2017, a new NIH policy mandated biomedical and behavioral "Clinical Trials" to be registered on ClinicalTrials.gov. In addition, NIH policies require personnel on NIH "Clinical Trials" to take GCP Training every three years.; 3) Registering may be required for Journal Publication (ICMJE). Please review relevant definitions [here](http://slu.edu/Documents/research/IRB/NIH_Clinical_Trial_Definition.docx). Contact the CTO at [contact] with questions about registering on ClinicalTrials.gov and refer to the [Training page of the IRB website](https://www.slu.edu/division-of-research-administration-home/institutional-review-board-(irb)/training-and-education) for information on NIH GCP Training requirements.

*** Subject Population ***

8. Subject Population - In the space below, please detail the participants that you are requesting to recruit (include description of each group requested)

a) Expected age range of subjects. (For example ≥ 18 yrs to 90 yrs).

≥ 18 yrs. and ≤ 50 yrs. and their infants
If a woman < 18 years old presented with a fetal tumor requiring open fetal repair, this would be done if deemed ethically sound by both CGCMC and SMHC ethics committees. Given this, then the patient may qualify for this study. This is a RARE event.

b) Number of evaluable subjects to be accrued at SLU or SLU site (this includes all sites under the direction of the SLU PI). 100 mothers and 100 infants

Exceeding the number listed here is a protocol violation. Prior IRB approval is required if additional participants are to be accrued. If applicable, this number should be consistent with your power analysis described in 3d.

c) Number of evaluable subjects to be accrued study wide. *?HELP?* 100 mothers and 100 infants

Protocol Title: Evaluation of Hysterotomy Site after Open Fetal Surgery

d) If including vulnerable populations (minors, pregnant women and fetuses, neonates, non-English speaking, economically or educationally disadvantaged, prisoners, adults temporarily or permanently unable to consent for themselves): 1) provide the rationale for the importance of including this population in the research, and 2) specify the measures being taken to minimize risks to potentially vulnerable subjects. Click on hyperlinks to access SLU Guidelines containing additional considerations and strategies for mitigating risks.

Since the study is a result of a fetal intervention, it is inherent to include fetuses and pregnant women.

If a woman < 18 years old presented with a fetal tumor requiring open fetal repair, this would be done if deemed ethically sound by both CGCMC and SMHC ethics committees. Given this, then the patient may qualify for this study. This is a RARE event.

e) If women, minorities, or minors are not included, a clear compelling rationale must be provided unless not applicable. Examples for not including minors: disease does not occur in children; drug or device would interfere with normal growth and development; etc. If federally funded reference appropriate section of the sponsors protocol/grant. *?HELP?*

This is secondary to the myelomeningocele protocol; women must be 18 years old or older. However, if a woman < 18 years old presented with a fetal tumor requiring open fetal repair, this would be done if deemed ethically sound by both CGCMC and SMHC ethics committees. Given this, then the patient may qualify for this study. This is a RARE event.

f) If any specifically targeted subjects are students, employees, or laboratory personnel, specify the measures being taken to minimize the risks and the chance of harm to these potentially vulnerable subjects. See SLU Guidelines for additional considerations and strategies for mitigating risks.

g) Describe how potential subjects will be identified for recruitment (e.g., chart review, referral from individual's treating physician, those individuals answering an ad). How will potential participants learn about the research, and how will they be recruited (e.g., flyer, e-mail, web posting, telephone, etc.)? Upload recruitment materials in the Attachment Section (#16). Important to remember: potential subjects cannot be contacted before IRB approval. NOTE: The use of SLU owned websites in an approved SLU format (e.g., Cancer Center website, etc.) are always approved methods of recruitment.

Subjects are referred to CG FCI by their OB or MFM for evaluation and consultation regarding their infant's abnormality. Women will be recruited for this study if they receive open fetal repair of that abnormality. A member of the research team will explain the study and answer all their questions. Women will be referred to [name] if questions or concerns persist.

*** Subject Population ***

8. Subject Population (continued)

Protocol Title: Evaluation of Hysterotomy Site after Open Fetal Surgery

Page numbers from a sponsor's protocol/grant may be referenced in 8h.

h) Inclusion and Exclusion Criteria.

Identify inclusion criteria.

FCI evaluation

Received Open Fetal Surgery

Open fetal surgery of myelomeningocele: maternal age of ≥ 18 yrs. and ≤ 50 yrs.

If a woman < 18 years old presented with a fetal tumor requiring open fetal repair, this would be done if deemed ethically sound by both CGCMC and SMHC ethics committees. Given this, then the patient may qualify for this study. This is a RARE event.

Agree to travel to Saint Louis for sonohysterogram 6 or more months after delivery.

Identify exclusion criteria.

Presently pregnant

Hysterectomy after delivery

Menopause

Using IUD (Intrauterine Device) for birth control

There is no exclusion criteria for infants

i) Compensation. Explain the amount and schedule of compensation, if any, that will be paid for participation in the study. Include provisions for prorating payment.

You will not be paid to take part in this study. However, travel and lodging expenses will be covered up to 400 dollars.

Travel distances will be calculated using Google maps.

If your primary residence is 50 miles or less you will receive a \$50 dollar VISA card.

If your primary residence is 51 to 100 miles you will receive a \$100 dollar VISA card.

If your primary residence is 101 to 150 miles you will receive a \$150 dollar VISA card.

If your primary residence is 151 to 200 miles you will receive a \$200 dollar VISA card.

If your primary residence is 201 to 250 miles you will receive a \$250 dollar VISA card.

If your primary residence is 251 to 300 miles you will receive a \$300 dollar VISA card.

If your primary residence is 301 to 350 miles you will receive a \$350 dollar VISA card.

If your primary residence is 351 miles or greater you will receive a \$400 dollar VISA card.

The costs of sonohysterogram and the pregnancy test used in this research study are provided at no cost to you or your insurance carrier. The costs are covered by a grant from the SSM Health St. Mary's Foundation and the Saigh Foundation.

Annual phone calls are made to you by a member of the research team to monitor pregnancy status until you become pregnant, have a hysterectomy or approach menopause.

j) Describe who will cover study related costs. Explain any costs that will be charged to the subject.

The costs are covered by a grant from the SSM Health St. Mary's Foundation and the Saigh Foundation, no costs will be charged to the subject. All study procedures and tests will be covered by SSM Health St. Mary's Foundation and the Saigh Foundation Grant including sonohystograms and pregnancy tests.

k) Estimate the probable duration of the entire study including data analysis and publication. This estimate should include the total time each subject is to be involved and the duration the data about the subject is to

Protocol Title: Evaluation of Hysterotomy Site after Open Fetal Surgery

be collected. If the study is Investigator-initiated, a timeline for individual subject recruitment, follow-up, total time for subject accrual, and data analysis for the study is required.

Subjects will be accrued for this study for 5 years maybe longer. We would like to follow subjects until they have another pregnancy, sterilization (a hysterectomy) or begun menopause. Completion of the study will take another 6 months. Analysis will take an additional year. Writing and publishing will take another year. We anticipate completion January 1, 2020.

It is intended that this study continue to move forward with patients throughout the existence of open fetal surgery at FCI. Similarly, if funding ends, the study would stop. Subjects will be accrued for this study in an ongoing manner. We anticipate annually accruing 15 new mothers participating in this study. We arbitrarily set the end date at 2020, however we may make an addendum to continue this study at that time.

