- This study will be discussed and all questions answered. If concerns persist they will be referred to [name] for clarification.
- The Study consent and HIPAA authorization will be signed.
- After open surgery she will be monitored and delivered appropriately, maintaining SOC.
- After the infant is born we will review the mother's and infant's electronic health records and FCI database records. (The datasheet is attached with the data points.) Gathering SOC information.
- She will be contacted by phone five months after giving birth and have a telephone interview by a member of the research team. This is part of the research plan and the list of conversational questions is attached. An appointment will be made for her to return for a sonohysterogram. (SLU Care IRB department is the SLU IRB or SSM Cardinal Glennon Fetal Care Institute)
- A reminder letter may be sent 2 weeks before appointment and a reminder phone call may be completed the day before the appointment.
- 6 months or more after delivery of an infant who has received open fetal repair the women will have a sonohysterogram to evaluate the healing process.
- i.600 mg of ibuprofen should be taken 1 to 2 hours before the procedure.
- ii. preferred timing is 1 week after menses.
- iii. A transcervical catheter is inserted in the uterus.
- iv. Small amount (approximately 20 ml to 100 ml) of sterile saline is introduced into the uterus.
- v. Ultrasound is used to evaluate the hysterotomy site.
- After the sonohysterogram the data sheet will be completed and information will be shared with the women. (Experimental)

Annual phone calls are made to the women to monitor pregnancy status until the conclusion of

Protocol Title: Evaluation of Hysterotomy Site after Open Fetal Surgery

the study. (Experimental)
If a pregnancy has occurred get a copy of the health and physical report(H&P) and the delivery report. (Experimental)

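### Section 8i ends the annual pregnancy calls when a woman becomes pregnant, while 3b continues them to study conclusion; under 8i some later deliveries would have no scheduled contact afterwards (minor)

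*Combined protocol and SAP*

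**What the plan says.** Three places in the current text govern contact after the scan.

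- **Section 3b (study procedures):** "Annual phone calls are made to the women to monitor pregnancy status until the conclusion of" the study. The next step is: "If a pregnancy has occurred get a copy of the health and physical report(H&P) and the delivery report". No stop at pregnancy is given, and no timing or trigger for the report request.
- **Section 8i (compensation):** the same annual calls run "to monitor pregnancy status until you become pregnant, have a hysterectomy or approach menopause".
- **Section 8k (duration):** "We would like to follow subjects until they have another pregnancy, sterilization (a hysterectomy) or begun menopause". This does not say whether follow-up includes the delivery.

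The secondary outcomes in 2b cover one or more future pregnancies. They include length of gestation, the condition of the fetal-surgery hysterotomy at a future delivery, and complications from dehiscence or rupture. Section 3d plans to correlate wall thickness with dehiscence, rupture or repair at cesarean delivery. Section 10a hopes that the scan will prove informative about risk in a later pregnancy.

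**The concern.** A woman who conceives cannot be under both rules. Under 3b she is called again the next year. Under 8i the call at which she reports a pregnancy closes the series. If she is still pregnant at that call, the delivery report does not yet exist, and nothing in the visible text schedules a contact to show when it does. If her first pregnancy miscarries, she leaves follow-up and a later pregnancy is not sought. Even if she has already delivered, any further pregnancy is missed, although 2b allows for more than one.

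At stake is the part of the study that relates the scan to later uterine outcome. Section 10a says no such data exist for this type of hysterotomy, and only later deliveries can supply them. Few can be expected, so each one counts. The rule was live: the amendment form records accrual closed on 22 May 2017 with participants still in follow-up.

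**Working it through.** The plan gives no figure to reproduce. The question is what share of later deliveries loses its scheduled contact if 8i replaces 3b. The same test must be applied to both rules: is there a scheduled call after the delivery?

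**Inputs from the documents.** Annual calls (3b, 8i). First approval on 26 March 2013 and closure on 20 December 2017 (event history). Accrual closed on 22 May 2017 with 35 accrued subjects (amendment form). Scan 6 months or more after delivery (3b).

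**Assumptions, none given in the documents.** Conception rate 0.05-0.20 per woman-year from the scan; pregnancy recognised at week 5-8; delivery at week 34-39; early loss 0-20%. Entry is spread evenly over the accrual period, with index delivery three months after entry, scan 6 or 12 months after that, and calls on the anniversary of the scan. The team learns of a pregnancy only at a call.

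**Step 1: share with no end-of-study limit.** Let G be gestation at delivery and r the time to recognition, both in years. With conception spread evenly, a call falls within a recognised pregnancy with probability G - r.

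- Weeks 34 and 8: (34 - 8)/52.18 = 0.50.
- Weeks 39 and 5: (39 - 5)/52.18 = 0.65.

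This overstates the difference between the rules. Near the end of the study, a pregnancy that is ongoing at a call has no later call under 3b either.

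**Step 2: same test under both rules, K annual calls per woman.** Count time from the scan and take the first later pregnancy, without loss.

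- A 3b call follows the delivery if conception falls between 0 and K - G.
- 8i drops the contact if the pregnancy is recognised and ongoing at one of calls 1 to K - 1. Each of these calls covers a conception window of width G - r.

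Share = (K - 1)(G - r)/(K - G), with weeks divided by 52:

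| Delivery, recognition (weeks) | K = 1 | K = 2 | K = 3 |
|---|---|---|---|
| 34, 8 | 0 | 0.500/1.346 = 0.37 | 1.000/2.346 = 0.43 |
| 37, 6 | 0 | 0.596/1.288 = 0.46 | 1.192/2.288 = 0.52 |
| 39, 5 | 0 | 0.654/1.250 = 0.52 | 1.308/2.250 = 0.58 |

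Few calls per woman are possible. Entry on 26 March 2013, delivery three months later and scan six months after that gives 26 December 2013. That is just under four years before closure, so three calls at most. Women consented retrospectively could have more.

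**Step 3: calendar simulation.** This adds staggered entry, early loss and repeat pregnancies, and requires a post-delivery call under both rules. With the December 2017 close:

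- About 35-55% of the deliveries that a 3b call would follow have no scheduled contact after delivery under 8i.
- This is roughly 0.3-3 deliveries per 35 women. If the 35 accrued subjects include infants (8b counts mothers and infants separately), there are about 35/2 = 17.5 women and the figure halves to roughly 0.15-1.5.

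**Step 4: sensitivity.** The date of the first annual call is not stated. The following use delivery at 37-40 weeks, recognition at 4-6 weeks, conception rates of 0.1 or 0.4 per year, and calls ending between December 2017 and January 2020:

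- First call 12 months after birth, first later pregnancy only: 0.59-0.73.
- First call at 18 months, first later pregnancy only: 0.37-0.58.
- Counting second and further deliveries too: 0.42-0.81.

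Delivery at 34 weeks with recognition at 8 goes down to about 0.30. The overall range is therefore about 0.3 to 0.8.

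**Step 5: credit the delivery-report request.** Section 8i does not cancel the 3b request. If every pregnancy found by a call leads to a delivery report under either rule, 8i loses only pregnancies after the first, including those after a miscarriage. The share falls to about 2-10%.

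**The case against.** The strongest reply is that 3b already orders the delivery report whenever a pregnancy has occurred, and 8i leaves that order in place. A call that finds an ongoing pregnancy can start the request. The telephone questions and the datasheet are attachments that are not available here and may hold a prompt to follow it up. This stands, and it is why the 35-55% counts missing scheduled contacts and is not a missing-data rate. What remains is a request with no timing and, under 8i, no later call to prompt it or to find a further pregnancy.

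A reader might infer that half to two-thirds of later deliveries are affected, because a call falls within a recognised pregnancy about that often. The documents do not support that as the headline: calls stop at study close under 3b too, and the same test under both rules gives the lower range.

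A reader might also count 8k as a second contradiction, or as lacking an end to follow-up. Neither is firm. Following a woman until another pregnancy can include its delivery. Section 8k also gives individual end events, then six months to complete, a year for analysis and a year for writing, and says "We anticipate completion January 1, 2020". Counting back two to two and a half years puts the end of data collection between about mid-2017 and January 2018. The date is loose ("We arbitrarily set the end date at 2020, however we may make an addendum to continue this study at that time"), but that is missing detail and not a separate defect. Since January 2020 includes analysis and writing, counts of deliveries up to that date are not a fair measure of what is at risk.

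Finally, the 8i sentence sits in the compensation answer, so 3b may well have governed in practice. The text does not say so.

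**Conclusion.** The contradiction between 3b and 8i is real and in the current text; 8k is ambiguous. If 8i is followed, about 35-55% of the later deliveries that a 3b call would follow have no scheduled contact after delivery, with a range of about 0.3 to 0.8 over other reasonable settings and about 2-10% once the report request is credited under both rules. Every rate behind these figures is assumed. A reader might infer that the deliveries would be lost; the documents support only that they are at risk. The study is descriptive and only secondary outcomes are touched, so this is a minor point.

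**What to change.** Reconcile 8i, and clarify 8k, to the rule that 3b already states: annual calls to study conclusion, continuing through and after each pregnancy, including one that miscarries. Give the report request its timing: the delivery report is requested after each delivery.

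The cost is a sentence in each section and a few extra annual calls to women who are pregnant or have delivered. The scan and the primary measurement do not change.

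### Do the 100 mothers in items 8b and 8c conflict with 15 a year for 5 years in item 8k?

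*Combined protocol and SAP*

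**What the plan says.** Items 8b (SLU sites) and 8c (study-wide) both give "100 mothers and 100 infants" as the number of evaluable subjects. The form's note under 8b adds "Exceeding the number listed here is a protocol violation".

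Item 8k gives the timeline in two paragraphs. The first says "Subjects will be accrued for this study for 5 years maybe longer", then lists the later steps: "Completion of the study will take another 6 months", "Analysis will take an additional year" and "Writing and publishing will take another year". It ends with "We anticipate completion January 1, 2020". The second describes accrual as continuing for as long as the fetal surgery programme and the funding last. It gives the rate, "We anticipate annually accruing 15 new mothers participating in this study", calls the 2020 end date arbitrary, and allows an addendum to continue.

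Three other places bear on the point:

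- Section 1a aims to scan all women evaluated at the institute who have had open fetal surgery.
- Section 13, item 1, describes a prospective consent route in clinic and a retrospective one by phone and mail. It gives no number for either.
- Section 3d calls the study descriptive, uses all patients, and states no power or precision target.

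**The concern.** 100 is the only size the plan states, and item 8k is the only place that gives a rate and a period. Multiplied together they give three quarters of it. Adding the later steps makes matters worse, because 100 mothers at that rate cannot be accrued, followed, analysed and published by the stated completion date. Women who are pregnant, have had a hysterectomy, have reached menopause or use an IUD (item 8h) cannot be scanned, so evaluable numbers would be lower than enrolled numbers.

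If the mismatch were real, a reader would expect more scanned women than the plan can produce. In a study whose output is a set of summary measures of scar thickness, size governs how precise those measures are.

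**Working it through.** **Inputs.** Stated size: 100 mothers (8b, 8c). Rate: 15 a year, base period 5 years, later steps 0.5 + 1 + 1 = 2.5 years, completion 1 January 2020 (8k). Start: 26 March 2013, the IRB approval in the Event History, since the form text in 8g bars contact before approval. No first-enrolment date is given.

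**1. The plan's own figure.** The plan does not derive 100, so the only test is rate × time. On the base period, 15 × 5 = 75. Shortfall: 100 − 75 = 25. Time for 100: 100 / 15 = 6.67 years, or 1.67 years beyond the base.

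**2. Against the completion date.** Approval to 1 January 2020 is 6.77 years.

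| Reading | Accrual time | Mothers at 15 a year |
|---|---|---|
| Base period | 5 years | 75 |
| Accrual up to 1 January 2020 | 6.77 years | 101.5 |
| All later steps finished by 1 January 2020 | 6.77 − 2.5 = 4.27 years | 64 |

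The base period plus later steps takes 5 + 2.5 = 7.5 years, ending about 24 September 2020. That is 7.5 − 6.77 = 0.73 years, about 9 months, past the stated date. For 100 mothers, 6.67 + 2.5 = 9.17 years ends about May 2022.

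**3. What would close the gap.** With 5 years of accrual, 25 retrospective mothers bring the total to 100. To keep 1 January 2020 with every later step, 100 − 64 = 36 are needed. Alternatively, 1.67 more years of accrual suffice, with a later end date.

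**4. Losses to scanning.** The plan gives no rate. Assuming 10% to 30% of enrolled mothers cannot be scanned, 100 evaluable needs 100 / 0.9 = 112 to 100 / 0.7 = 143 enrolled (rounded up). On the 5-year base that means 112 − 75 = 37 to 143 − 75 = 68 retrospective mothers.

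**5. Scale of the effect.** For a mean with the same spread, the standard error at 75 rather than 100 is √(100/75) = 1.15 times as large. At 64 it is √(100/64) = 1.25 times as large. Section 3d sets no precision target for either to miss.

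**The case for a change.** The strongest case for a change has four parts.

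First, item 8k asks investigator-initiated studies for the total accrual time, and an open-ended extension is not a total. This stands: the extra 1.67 years appear nowhere.

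Second, the reading that reaches 101 by accruing up to 1 January 2020 leaves no room for completion, analysis or writing. Nor could the last mothers enrolled be scanned by then, because the scan comes 6 months or more after delivery. Even ignoring the remaining gestation, (6.77 − 0.5) × 15 = 94 is the most that could be. This also stands, so that reading does not rescue the completion date.

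Third, the retrospective route has no stated number, and nothing says outright that those mothers are additional to the 15 a year. This stands as an omission. However, the rate is worded for new mothers, and section 1a covers all women who have had the surgery at the institute. A total of 75 new mothers plus about 25 earlier ones is a natural reading, before any loss to scanning.

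Fourth, if 100 is only a ceiling, the plan gives no expected size. This is weaker. The rate and base period give about 75 new mothers, and a ceiling above expected accrual is normal. What is missing is the retrospective part.

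**Conclusion.** No change to the plan follows. The arithmetic is right, but it multiplies the rate by the shortest period the plan allows and leaves out a recruitment route the plan describes. The plan is not shown to miss 100; it does not say how it would get there. What remains unstated is either about 25 retrospective mothers (more after losses to scanning) or about 1.7 years of further accrual. The completion date is also about 9 months too early for the plan's own steps, though the plan itself calls the 2020 end date arbitrary and extendable.

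None of this touches an analysis. The summaries in section 3d are computed on whoever is available, and no test, interval width or stopping decision was set with 100 in mind. The Amendment form records 35 accrued subjects and accrual closed on 22 May 2017, and the Event History shows the study closed on 20 December 2017. Rewording 8b or 8k now would alter nothing. A report will in any case give the numbers accrued and scanned, and those determine the precision achieved.

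The dates assume accrual from IRB approval at a constant 15 a year. Starting from form submission (4 January 2013) or form creation (10 September 2012) gives 67 or 72 mothers after the later steps, so the picture does not change. The reading that closes the gap assumes that retrospective mothers are additional to the 15, which the wording suggests but does not state.
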